## 5. Trial Population

### 5.1. Screening data

We will tabulate the total number screened, enrolled, and excluded (along with the reasons for exclusion).

### 5.2. Eligibility

The eligibility criteria for Trial I and Trial II are listed in section 5 (study population) of the clinical protocol.

### 5.3. Recruitment

We will report the number of participants screened, enrolled, randomized, treated, and measured at the primary endpoint with reasons for exclusion at each step for Trial I and Trial II.

### 5.4. Withdrawal/follow-up

We will tabulate the number of participants who withdraw, the number who die, and the number who are lost to follow-up before the primary outcome assessments in each Trial.

### 5.5. Baseline patient characteristics

We will report baseline characteristics by group, including sex, age in years, and clinical characteristics at enrollment.

## 6. Analysis

### 6.1. Outcome definitions

Trial I: Primary Endpoint: Log-transformed viral load after 7 days of treatment

Secondary Endpoints:

- Anterior chamber cell (days 7, 21)
- Intraocular pressure (days 7, 21)
- Visual acuity (days 7, 21)
- Controlled inactivity defined as  $\leq 0.5+$  anterior chamber cell AND intraocular pressure  $< 24$  mmHg AND no cornea edema AND no active KPs (day 7, 21).

Trial II: Primary Endpoint: Proportion recurrent inflammation ( $\geq 1+$  anterior chamber cell at any study visit) over 12 months

Secondary Endpoints:

- Prevalence of CMV associated with recurrence of uveitis

1a. The Aim 1 primary outcome **viral load after 7 days of treatment** will use the results from quantitative PCR at 7 days of treatment or placebo therapy (day 7 of trial). All quantitative PCR viral loads will undergo base-10 logarithm-transformation, with units converting from IU/mL to log IU/mL. Log-transformed viral loads will be used because the range of viral loads can be wide and dealing with very large and very small numbers is handled more efficiently using a logarithmic scale. Such normalization of the distribution of viral loads is consistent with standard practice in viral load analyses.

1b. **Clinical outcomes and inactivity:** At each study visit participants will be clinically examined for ocular outcomes including AC inflammatory cells, intraocular pressure, and visual acuity. A study ophthalmologist will make a clinical determination as to whether the patient's inflammation is considered inactive. Clinical outcomes and the proportion of participants that

achieve quiescence by day 7 and 21 will be compared by arm. Patients will also be administered a questionnaire querying when they felt symptomatic improvement in their condition. This analysis will be viewed as hypothesis generating and will be treated as supplementary and in addition to the main finding.

**2a. Proportion recurrent inflammation over 12 months:** After achieving clinical quiescence, participants will be offered enrollment in Trial II where they would be randomized to long-term suppressive therapy to study the effect on recurrence rate of anterior uveitis. Each participant will be assessed for recurrence at each monthly visit during the 12 months or, alternatively, if participant's experience symptoms of a recurrence, then they will be instructed to call the local site's clinical coordinator to be scheduled for an evaluation within 1 to 2 days. Recurrence of uveitis in CMV is mostly typically symptomatic, so having participants call us is expected to be an effective strategy for catching recurrence of uveitis. If recurrence occurs, aqueous chamber fluid will be collected from participant at the time of recurrence to quantify viral load.

**2b. Prevalence of CMV associated with recurrence of uveitis:** Aqueous fluid obtained in participants exhibiting recurrence of uveitis during Trial II will be submitted for directed polymerase chain reaction testing to determine the proportion of uveitis flares associated with CMV (as compared to “sterile” inflammation).

**3a. Prevalence of mutations conferring antiviral resistance:** The analysis population will include individuals enrolled in both Trials I and II who are randomized to receive oral or topical antivirals in Trial II and experience a recurrent infection. Among patients that experience a recurrent infection (anticipated n=34, see Sample Size section 3.3), we will compare the proportion of infections with antiviral mutations upon recurrence with the proportion with antiviral mutations at baseline.

**3b. Pathogens other than CMV and host transcriptional profile:** (i) In aqueous we will describe the host transcriptional profile in participants with CMV anterior uveitis entering Trial I and in those who fail to enter Trial I due to having negative CMV PCR testing. (ii) We will identify and describe non-CMV pathogens in cases unable to enter Trial I. (iii) We will describe host transcriptional profile in participants during Trial II who have recurrent inflammation.

## 6.2. Analysis methods

Patients will be analyzed according to their assigned treatment (intention-to-treat).

### Primary Analysis Trial I

*Aim 1a.* The primary analysis will compare **viral load at 7 days** between each study arm. The Aim 1 treatment effect will be reported as a difference in log IU/mL between the two arms.

We will model mean log viral load using linear regression that includes indicators for treatment arm, indicators for each site used to stratify the randomization, and baseline viral load. We will additionally estimate max-T simultaneous confidence intervals and p-values adjusted for the two

pair-wise comparisons (*oral valganciclovir* vs. *topical ganciclovir 2%*, *oral valganciclovir* vs. *placebo*).

We will examine residuals for approximate normality and to check for outliers and will report the variance within each arm.

Primary analyses will be repeated using multiple imputed datasets as described in Section 6.3 when missing data thresholds are met.

### Secondary Analyses Trial I

**Aim 1b. Clinical outcomes and inactivity:** We will compare the clinical outcomes and the proportion of patients that reach clinical inactivity by day 7 and by day 21 in the three treatment arms. We will estimate the difference in proportion using a linear or log-binomial regression model, as appropriate, that includes indicators for treatment arms, indicators for each site used to stratify the randomization, and baseline viral load. We will use marginal predictions from the regression models to estimate the difference in proportion. We will report max-T simultaneous confidence intervals and p-values adjusted for the two pair-wise comparisons (*oral valganciclovir* vs. *topical ganciclovir 2%*, *oral valganciclovir* vs. *placebo*).

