- Laboratory screening orders (CBC, chemistry panel, pregnancy test, HIV status)
- Patients will be prescribed topical corticosteroid (prednisolone acetate 1%) to be used one drop in affected eye four times per day (this is typical standard of care)
- Patients requiring management of elevated IOP will be prescribed IOP-lowering medication according to treating ophthalmologist's discretion and best medical judgment

Exam 1 Randomization and Procedures

[figure not shown]
- Review of results of in- house CMV PCR and laboratory results
- Consent, enrollment, randomization to treatment arm if participants meet eligibility criteria
- Clinical eye examination (in the following order: visual acuity, slit lamp examination of anterior segment, intraocular pressure assessment, confocal microscopy)

Randomization to 1 of 3 arms

Exam 2 (Day 7) Follow-up

- Clinical eye examination (in the following order: visual acuity, slit lamp examination of anterior segment, intraocular pressure assessment)
- **Anterior chamber paracentesis #2**
- **Assessment of clinical quiescence (grading anterior chamber cell)**
- Laboratory monitoring orders (complete blood count, complete metabolic panel)

Exam 3 (Day 21) Final visit for trial I

Trial II

**Exam 1
(Re-randomization)**

Clinically inactive (< 1+ anterior chamber cell)
for at least 2 weeks with at least 2 weeks
wash-out period (no antivirals)

- Clinical eye examination (in the following order, VA, slit lamp examination of anterior segment, IOP)
- **Suppressive treatment initiation (randomized to 1 of 3 arms)**

Group 1: Oral
valganciclovir N=35

Group 2: Topical
ganciclovir 2% N=35

Group 3: Placebo
N=35

**Exam 2
(1 month after
randomization)**

- Clinical eye examination (in following order, VA, slit lamp examination of anterior segment, IOP)
- **Assessment for recurrence of inflammation**
- **Anterior chamber paracentesis #3 if recurrent inflammation (participant exits study if recurrent inflammation)**

**Exam 3
(3 months after
randomization)**

- Clinical eye examination (in following order, VA, slit lamp examination of anterior segment, IOP)
- **Assessment for recurrence of inflammation**
- Confocal or specular microscopy if recurrent
- **Anterior chamber paracentesis #3 if recurrent inflammation (participant exits study if recurrent inflammation)**

**Exam 4
(5 months after
randomization)**

- Clinical eye examination (in following order, VA, slit lamp examination of anterior segment, IOP)

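### The SAP states no model for Trial I anterior chamber cell, IOP or visual acuity, and names their Exam 1 values as covariates nowhere; adding them would gain precision

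*SAP*

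**What the plan says.** SAP 6.1 lists four Trial I secondary endpoints at days 7 and 21: anterior chamber cell, IOP, visual acuity, and a composite of controlled inactivity (cell at most 0.5+, IOP below 24 mmHg, no corneal edema, no active keratic precipitates).

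SAP 6.2, Secondary Analyses Trial I (Aim 1b), opens with the comparison to be made: "We will compare the clinical outcomes and the proportion of patients that reach clinical inactivity by day 7 and by day 21". The model follows: "We will estimate the difference in proportion using a linear or log-binomial regression model, as appropriate", and it is one "that includes indicators for treatment arms, indicators for each site used to stratify the randomization, and baseline viral load". Marginal predictions then give the difference in proportion. No other model is given under Aim 1b.

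The Exam 1 values exist. The protocol schema has the clinical eye examination at the randomization visit cover "visual acuity, slit lamp examination of anterior segment, intraocular pressure assessment, confocal microscopy". Protocol 7.1.1 says that the slit lamp examination assesses anterior chamber cell, and Protocol 7.1.3 has the eye exam form completed at every exam.

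**The concern.** Two of the three measures, IOP and acuity, are continuous and the third is a graded scale, yet the only model written is for a proportion. How they will be analysed, and with which covariates, is left open until the data are in.

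The plan also leaves unused the covariate most likely to help. For viral load, SAP 3.3 reduces the planning SD from 0.98 to 0.66 because the primary model adjusts for that outcome's own baseline. The same reasoning is not carried to the clinical outcomes, although their baselines cost nothing further to collect.

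What is at stake is the width of the intervals for secondary outcomes with about 35 participants per arm, and the prespecification of their models. SAP 6.1 describes the 1b analysis as hypothesis generating, but SAP 4.1 makes inflammation control a key secondary endpoint inside the gatekeeping procedure, so at least the inactivity model should be settled in advance.

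**Working it through.** **1. Where could an own-baseline adjustment enter?**
- SAP 6.2, Aim 1b: arm, site and baseline viral load, attached to the difference in proportion.
- SAP 6.2, Sensitivity Analyses: extra covariates, but only in a secondary analysis after a chance imbalance. Age, sex and prior prednisolone use are the examples; cell, IOP and acuity are not named. The list is open, so they could be admitted.
- SAP 6.4: the change-score analysis is for Aim 1a only.
- SAP 6.3 and Protocol 8.3.1: baseline characteristics may be used as predictors of missing data. None of the three is named.
- Protocol 8.3, item 1b: proportions compared by arm, with no covariates stated.

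**2. The plan's own figure for the principle.** The inputs in SAP 3.3 are SD 0.98, correlation with own baseline 0.74, difference 0.50 log10, two-sided alpha 0.025 and power 80%.
- SD_r = 0.98 × √(1 − 0.74²) = 0.98 × √0.4524 = 0.659, matching the stated 0.66.
- A two-sample t-test (noncentral t) needs 35 per arm, with power about 0.81.
- 35 / 0.90 = 38.9, so 39 per arm, and 3 × 39 = 117.

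The SAP figure reproduces. (The protocol quotes a correlation of 0.50, which gives SD_r 0.849, not 0.66; that is a separate conflict.) Neither document gives a power or precision figure for the clinical outcomes.

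**3. Gain for a continuous clinical outcome.** Let r_own be its correlation with its own Exam 1 value and r_VL its correlation with baseline viral load. Both are assumed. The variance with own baseline relative to the variance with viral load is

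(1 − r_own²) / (1 − r_VL²),

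and the standard error (SE) changes by the square root of this ratio. The equivalent sample size is 35 divided by the ratio.

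| r_own | r_VL | Variance ratio | SE change | Equivalent n per arm |
|---|---|---|---|---|
| 0.3 | 0 | 0.910 | −4.6% | 38.5 |
| 0.3 | 0.2 | 0.948 | −2.6% | 36.9 |
| 0.5 | 0 | 0.750 | −13.4% | 46.7 |
| 0.5 | 0.2 | 0.781 | −11.6% | 44.8 |
| 0.7 | 0 | 0.510 | −28.6% | 68.6 |
| 0.7 | 0.2 | 0.531 | −27.1% | 65.9 |
| 0.1 | 0.2 | 1.031 | +1.6% | 33.9 |

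At 35 per arm, 80% power and two-sided alpha 0.025, the detectable difference is 0.751 SD unadjusted and 0.736 SD with viral load (r_VL = 0.2). With own baseline it is 0.716, 0.650 and 0.536 SD for r_own = 0.3, 0.5 and 0.7.

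**4. Replace viral load or keep it?** A simulation used 3 × 35 participants, 6 sites, 4000 runs and an assumed correlation of 0.2 between own baseline and viral load. SE changes are relative to viral load alone.

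| r_own, r_VL | Own baseline only | Both covariates |
|---|---|---|
| 0.3, 0.1 | −4.2% | −3.8% |
| 0.5, 0.2 | −12.1% | −12.0% |
| 0.7, 0.2 | −27.9% | −27.6% |
| 0.1, 0.2 | +1.4% | +0.2% |

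Keeping both gives almost the full gain and nearly removes the penalty when own baseline is a weak predictor.

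**5. The inactivity proportion.** Trial I requires at least 1+ cell and excludes inactive uveitis (Protocol 5.1 and 5.2), so every participant counts as not inactive at entry. The endpoint has no own baseline that varies; only components such as Exam 1 cell grade and IOP can be added.

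**The case against.** A reader might infer that the SAP adjusts IOP, acuity and cell grade for baseline viral load instead of for their own baselines. The text does not say so. The covariate clause belongs to the sentence on the difference in proportion, and extending it to the measured outcomes is an inference from the Aim 1b heading. Read literally, those outcomes have no model at all. Both readings call for the same correction.

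A reader might also infer bias, with chance baseline differences passing uncorrected into the result. Randomization keeps the contrast unbiased, and its interval already allows for chance imbalance.

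It is also tempting to take r² as the gain, which at r_own = 0.5 would equal a third more patients. That compares own baseline with no baseline covariate. If viral load is already in the model, the figure depends on r_VL as well: at r_VL = 0.2 it is 44.8 / 35, or 28% more. The formula is for linear models and does not transfer directly to ordinal or log-binomial analyses.

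The strongest remaining objection is that nothing in the documents shows how well Exam 1 values predict days 7 and 21. Topical corticosteroid, and IOP-lowering medication where needed, are prescribed at Exam 0, so cell and IOP may already be changing at Exam 1. The entry threshold also truncates the range of cell grade. This stands: the size of the gain is uncertain and may be small for cell. The chance-imbalance analysis is a partial answer, but it is conditional and secondary and does not name these baselines. The stakes are modest, since IOP and acuity are outside the SAP 4.1 testing hierarchy.

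**Conclusion.** The point holds as a gap in specification and a missed gain in precision. Cell, IOP and acuity have no stated model, and their Exam 1 values are named in none. For continuous outcomes the SE would fall by about 3–5%, 12–13% or 27–29% at r_own = 0.3, 0.5 or 0.7, relative to adjusting for viral load alone with r_VL of 0 to 0.2. All these correlations are assumptions. The gain disappears if own baseline predicts no better than viral load. No gain has been sized for graded cell or for binary inactivity. The validity of the Trial I comparisons and the primary analysis are unaffected. This is a minor but nearly free improvement.

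**What to change.** In SAP 6.2, Aim 1b, state a model for each measured outcome at days 7 and 21 with arm, site, baseline viral load and that outcome's own Exam 1 value:
- IOP: linear regression.
- Visual acuity: linear regression after conversion from Snellen to logMAR.
- Anterior chamber cell: a model suited to the graded scale (ordinal regression is one choice), with a summary that fits the absolute-scale reporting in SAP 4.1.

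In the inactivity model, add Exam 1 cell grade and IOP to the existing covariates. The planned marginal predictions still deliver the difference in proportion. Keep baseline viral load throughout.

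The cost is SAP wording and one or two extra model terms. No new data, visits or participants are needed. The change should be made before unmasked outcome data are seen.

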### Primary Analysis Trial II

**Aim 2a. Recurrence rate of anterior uveitis over 12 months:** The proposed analysis for sub-Aim 2a (Trial II), which is a clinical outcome, is a log-binomial regression model to compare cumulative inflammatory recurrence (based on anterior chamber cell  $\geq 1+$  cell) between treatment groups. We will censor participants at the first recurrence of anterior uveitis (based on anterior chamber cell  $\geq 1+$  cell) or 12 months. The model includes indicators for the treatment arm and indicators for each site used to stratify the randomization. We will estimate the risk ratios from the model for the two primary comparisons, *oral valganciclovir* vs. *topical ganciclovir 2%*, and *oral valganciclovir* vs. *placebo*. We will use a simulation-based permutation test to estimate p-values, and will report max-T simultaneous confidence intervals and p-values adjusted for the two pair-wise comparisons (*oral valganciclovir* vs. *topical ganciclovir 2%*, *oral valganciclovir* vs. *placebo*). Pre-specified sub-group analyses by sex will be performed.

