2b: We hypothesize that aqueous obtained at the time of a recurrence of inflammation will demonstrate a detectable viral load and will correlate with level of inflammation.

Specific Aim 3 (samples from Trials I and II): To characterize host transcriptional signatures and viral genomic features in CMV anterior uveitis using RNA sequencing of aqueous samples.

3a: We hypothesize participants completing both trials who exhibit recurrent inflammation after antiviral suppression (Trial II) will have a higher prevalence of CMV mutations associated with antiviral resistance compared to baseline samples (Trial I).

3b: We hypothesize that (i) host transcriptional profiles will distinguish CMV anterior uveitis from anterior uveitis cases negative for CMV and unable to enter Trial I, (ii) we will identify non-CMV pathogens in cases unable to enter Trial I, and (iii) we will identify unique signatures associated with recurrent inflammation in Trial II participants.

Study Population:

We plan to enroll 117 participants (39 participants per arm) across all sites.

Description of

Sites/Facilities

Enrolling

Participants:

Participants will be enrolled at 6 sites centered in the United States, Thailand and Taiwan. In Thailand, participants will be enrolled at Chulalongkorn University in Bangkok, Thailand, Khon Kaen University in Khon Kaen, Thailand and Chiang Mai University in Chiang Mai, Thailand. In Taiwan, participants will be enrolled at

Chang Gung Memorial Hospital. In the United States, participants will be enrolled at the Francis I. Proctor Foundation/UCSF and the University of California, Los Angeles. UCSF will serve as the clinical and data coordinating center.

Outcomes:

Trial I: Primary Endpoint: Viral load after 7 days of treatment

Secondary Endpoints:

- Clinical quiescence

Trial II: Primary Endpoint: Recurrence of inflammation over 12 months

Secondary Endpoints:

- Prevalence of mutations conferring antiviral resistance

Schema

Trial I

Pre-study visit (Exam 0)

Clinical eye examination reveals active anterior uveitis ($\geq 1+$ AC cell) and suggests a viral aetiology

[figure not shown]
- **Anterior chamber paracentesis** is performed to establish a viral aetiology
 - Half of fluid will be used for in- house directed PCR for HSV, VZV and CMV
 - At least 50 μ L of fluid will be preserved and used for quantitative CMV PCR to be conducted at a single US laboratory in eligible participants

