## **4. Statistical Principles**

### **4.1. Confidence intervals and P-values**

The primary analysis for Trial I and Trial II will be conducted with a two-sided alpha of 0.05/2 = 0.025 to account for the two primary comparisons of interest (*oral valganciclovir* vs. *topical ganciclovir 2%*, *oral valganciclovir* vs. placebo). We will report 95% confidence intervals for the estimated differences between groups, on an absolute scale.

We will use a single-step, max-T approach to estimate p-values adjusted for multiple comparisons in each analysis. Alongside unadjusted p-values and 95% confidence intervals, we will present max-T adjusted p-values and simultaneous 95% confidence intervals for differences that account for multiple comparisons.

We will employ a multiple testing hierarchical approach in the following manner:

1. Primary endpointss (alpha = 0.025 each trial)
  - a. Trial I: viral load comparison
  - b. Trial II: Number of recurrences comparison
2. Key secondary endpoints (alpha = 0.025 shared):
  - a. Inflammation control
  - b. Antiviral resistance mutations

Gate-keeping procedure:

Primary endpoints must be significant before testing secondaries

Holm-Bonferroni correction within each family

Truncated testing if primary endpoint non-significant

Family-wise error rate controlled at 0.05 using:

Separate error rates for each trial

Sequential gatekeeping

Multiplicity adjustment within families

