### Sensitivity Analyses

In all analyses, model adequacy will be checked by examination of residuals or other goodness of fit tests as needed. Inadequate model fit will prompt us to report alternative models. If there are chance imbalances in prognostic baseline patient characteristics, including age, sex, and prednisolone use prior to enrollment, a secondary analysis will include them as covariates in the regression model.

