# 8. Revision history

Version	Date	Summary of Changes, Justification, and Timing vis-à-vis key trial events (enrollment completion, interim analyses, unmasking, etc)
1	2021-05-13	First version

2	2022-05-24	
 
Added pre-specified subgroup analyses by sex and by study site (section 6.4)
 
Added per-protocol analysis (section 6.4)
 
Added analyses of specific gene mutations (section 6.4)
 
Added details for interim analysis scenarios (section 3.5)
 

3	2025-01-15	
 
Updated sample sizes for Trial I and II based on results from prior trial and studies (section 3.3)
 
Changed primary aims for Trial II and updated the statistical methods accordingly (section 6.1, 6.2)
 
Removed per-protocol analysis because all participants adhered to their assigned treatment; removed subgroup analysis by site because there was one site with only a few participants, which would not provide sufficient statistical power for a meaningful analysis (section 6.4)
 

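### The Trial II primary log-binomial model will often have its maximum on the boundary, and the SAP fixes no fitting method, permutation statistic or named fallback for that case

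*SAP*

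**What the plan says.** SAP 6.2, Primary Analysis Trial II (Aim 2a), states that the proposed analysis "is a log-binomial regression model to compare cumulative inflammatory recurrence" between arms. On covariates: "The model includes indicators for the treatment arm and indicators for each site used to stratify the randomization". Risk ratios are estimated for oral versus topical and oral versus placebo. On inference: "We will use a simulation-based permutation test to estimate p-values, and will report max-T simultaneous confidence intervals and p-values", adjusted for those two comparisons.

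SAP 4.1 promises 95% confidence intervals "for the estimated differences between groups, on an absolute scale". SAP 3.3 expresses the Trial II sample size in percentage points.

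The only provision for a model that does not fit is a general sentence under Sensitivity Analyses: "Inadequate model fit will prompt us to report alternative models". No algorithm, starting values, permutation statistic or alternative model is named. SAP 6.6 specifies R, version 4.0 or higher, and nothing more on fitting.

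On sites, the Protocol synopsis says "Participants will be enrolled at 6 sites centered in the United States, Thailand and Taiwan". Expected site sizes are not given. The SAP revision history does say that it "removed subgroup analysis by site because there was one site with only a few participants", which points to uneven recruitment.

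**The concern.** A log link does not keep fitted risks below 1. With a high-risk arm and several small sites, the likelihood is often maximised where at least one arm-by-site combination has a fitted risk of exactly 1. Standard unconstrained fitting may then stop or not converge. The usual information-based standard errors, on which max-T simultaneous intervals normally rest, also no longer apply.

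This is the primary analysis of Trial II, and SAP 4.1 makes the secondary endpoints conditional on the primaries. If the analyst has to decide after seeing the data how to fit the model, what to permute or which model to substitute, that choice can affect the primary result. A plan that claims family-wise error control should not leave it open.

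**Working it through.** **Inputs.** Evaluable participants: 28 per arm, 84 in all (SAP 3.3). Placebo risk: 25% (SAP 3.3, Protocol 8.2). Oral risk: 65% (SAP 3.3), 61% from the Protocol's 36-point difference (25 + 36), 60% from the Aim 3 recurrence assumption, and 75% in the source study cited in SAP 3.3 (9/12). Allocation: 1:1:1 within site. Sites: six.

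Assumed, because the documents do not say: site sizes, topical risk (varied from 25% to 65%), no true site effect, complete cases only.

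**Step 1: the plan's own figure.** At 25% versus 65%, 28 per arm and two-sided alpha 0.025 (z = 2.241):
- pooled SE = √(2 × 0.45 × 0.55 / 28) = 0.1330
- unpooled SE = √((0.25 × 0.75 + 0.65 × 0.35) / 28) = 0.1217
- power = Φ((0.40 − 2.241 × 0.1330) / 0.1217) = Φ(0.84) = 0.80

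So the SAP's 40 points reproduces. The Protocol's 36 points gives power of about 0.70 at 28 per arm; the two figures need reconciling separately.

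**Step 2: why the boundary is close.** The model is log(risk) = intercept + arm + site. It has 1 + 2 + 5 = 8 parameters for 18 arm-by-site cells, and 84/18 = 4.7 participants per cell on average. If the oral risk is 65%, a site can have a fitted risk at most 1/0.65 = 1.54 times the average before its oral cell reaches 1. Chance variation in small sites reaches that limit easily.

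**Step 3: how often.** Simulation used 1000 datasets per scenario. The log-likelihood was maximised subject to all fitted risks being at most 1, and a maximum was called boundary when a fitted risk reached 1. Monte Carlo standard error is about √(0.5 × 0.5/1000) = 1.6 points.

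| Assumed site sizes | Oral 65%, topical 25–65% | Oral 61% | Oral and topical 60% | Oral 75% |
|---|---|---|---|---|
| Six equal (14 each) | 46–56% | 42–45% | 41% | 78–83% |
| 28/20/14/10/8/4 | 62–67% | 57–60% | 53% | 82–89% |
| 36/24/12/6/4/2 | 74–80% | 74–75% | 73% | 92–93% |
| Four equal (21 each) | 17–25% | not run | not run | not run |

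Further runs of the same set-up agree. With six equal sites they gave 44–55% and 50–54% at oral 65%, and 35–37% at 60–61%. With uneven sites they gave 55–66% and 64–68% at oral 65%, and 53–55% at 60–61%. Over 60–65% risk and six sites the range is therefore about 35–80%. It drops to 12–34% when both active arms are at 45%, and to 2–7% when all three arms are at 25%.

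Sites with no events are a separate problem, because their coefficient goes to minus infinity. Counting them too raises the oral-65% figures to 66–74% (28/20/14/10/8/4) and 87–94% (36/24/12/6/4/2).

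**Step 4: what standard fitting does.** A re-implementation of R-style iteratively reweighted fitting with step-halving was run on 400 datasets per scenario (standard error up to 2.5 points), six sites, oral 65%. With default starting values it stopped for lack of valid coefficients in 82–93% of datasets. That is partly a starting-value problem, distinct from the boundary. With a supplied start, 25–64% still did not converge.

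**Step 5: what a constrained fit does.** In the same datasets the constrained maximum gave finite arm risk ratios in 99.75–100%. Within-site permuted data reached the boundary less often: 5–15% with equal sites and 14–39% with uneven sites. Ten complete permutation tests (199 permutations each, six equal sites, risks 65/45/25%) all returned a p-value with no undefined permutation, although the observed data were on the boundary in seven of them.

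**Step 6: does the replacement matter?** Modified Poisson, logistic and linear probability models, applied to oral versus placebo at two-sided 0.025, disagreed on significance in about 5–10% of simulated 84-participant trials.

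**Step 7: interim.** SAP 3.5 plans an efficacy look ideally at 15 per arm and names no other model. With 45 participants, the maximum was on the boundary in 78–88% of datasets at 61–65% oral risk.

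**The case against.** A reader might infer that the Trial II primary estimate and its p-value usually cannot be computed, and that a post-hoc model would replace the planned one in most cases. The documents do not support either reading.

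- A boundary maximum is still an estimate. Step 5 shows that constrained fitting of the same model gives finite risk ratios and usable permutation p-values. The SAP does not prescribe default starting values or unconstrained fitting, so the failure rates in step 4 describe one possible implementation.
- Whether the boundary is the usual outcome depends on inputs that the documents do not give. The 65% is a detectable-effect value, not a forecast, and the topical risk is nowhere stated. With six equal sites the rate is about a coin flip at 65% and below half at 60–61%. With four equal sites it is a minority; the synopsis's study description lists four institutions, although the site description says six.
- The 84 is not a ceiling. Protocol 4.1 and SAP 2.1 let inactive patients enter Trial II directly. Raising the total to 120 (an assumption) with six equal sites lowered the rate at 25/65/65% from 52% to 29%.
- The scale mismatch does not show that the model fails. A risk difference can be obtained from a log-binomial fit by marginal prediction, as SAP 6.2 does for Aim 1b.

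All of this stands as a limit on size. It does not answer the remaining gap: the SAP specifies neither the constrained fit nor the permutation statistic, information-based intervals are unreliable at the boundary, and the fallback is unnamed.

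**Conclusion.** The concern holds in a conditional form. At 60–65% active-arm risk with six sites and 84 evaluable participants, the planned model has its maximum on the boundary in roughly 35–80% of simulated datasets. The rate is lower at lower risks, with fewer sites or with more participants, and higher at the source study's 75%. In those datasets unconstrained fitting often fails and the max-T intervals lose their basis, while point estimates and permutation p-values remain obtainable by methods the SAP does not specify. The result rests on assumed site sizes and topical risks and on no true site effect.

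Separately, and without simulation, Aim 2a reports risk ratios while SAP 4.1 promises absolute differences and the sample size is in percentage points.

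This should be fixed. It is a gap in the specification of a primary analysis, not evidence that Trial II cannot be analysed.

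**What to change.** Replace the Aim 2a primary model with one pre-specified estimator: logistic regression on arm and site, followed by marginal standardisation. Report the risk difference as the primary scale, in line with SAP 4.1 and the sample size, and the risk ratio alongside it. The SAP already uses marginal predictions for Aim 1b.

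- **P-values.** Take both max-T adjusted p-values from a single within-site re-randomisation distribution of the two contrasts. Name the statistic, including whether it is studentised.
- **Intervals.** Obtain the simultaneous intervals from the standardised estimates, and name the variance method.
- **Sparse sites.** State how sites with no events or all events are handled, because a logistic model with site indicators is affected too. One option is to pool small sites under a rule fixed before unmasking.
- **Interim.** Say whether the same estimator is used at the interim look.
- **Sensitivity analysis.** Modified Poisson with robust variance may be named here. It targets a conditional common risk ratio and can give fitted risks above 1, so it is not equivalent to the standardised logistic estimate.

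The cost is SAP wording and analysis code. No change to data collection or sample size is needed.
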